5. REMOVAL OF PARTICIPANTS FROM STUDY TREATMENT OR ASSESSMENT

5.1. Discontinuation from Study Treatment

A participant's double-blind treatment may be discontinued for any of the following reasons:

- Adverse event that in the judgement of the Investigator and/or Medical Monitor indicate the participant should not continue study treatment
- Participant noncompliance with the protocol or study treatment that is considered significant by the Medical Monitor
- Investigator decision
- Withdrawal by participant
- Lack of efficacy
- Lost to follow-up
- Study termination by Sponsor
- Other, non-adverse event

A participant's double-blind treatment must be discontinued for any of the following reasons:

- Decline in PFT values (FEV₁ and/or FVC) below 50% of the predicted values
- Confirmed diagnosis of clinically significant macular edema
- Confirmed diagnosis of active TB
- Participants who have a cardiovascular treatment-related symptomatic event (eg, chest pain, dizziness, palpitations, lightheadedness, shortness of breath, or syncope) associated with reduction of the HR or associated with clinically relevant ECG changes at any time during the 4-hour monitoring period on Day 1 or Day 2 (as applicable) (Section 9.4.2.1)
- Participants who have not met the discharge criteria ([Table 3](#)) on Day 1 after \geq 4 hours of extended monitoring, or Day 2 by 4 hours postdose
- Pregnancy (Section 9.9.9)

- Suspected drug induced liver injury as defined by the 2009 FDA Guidance for Industry ([FDA 2009](#))
 - ALT or AST $> 8 \times$ ULN
 - ALT or AST $> 5 \times$ ULN for > 2 weeks
 - ALT or AST $> 3 \times$ ULN and (total bilirubin $> 2 \times$ ULN or international normalized ratio > 1.5)
 - ALT or AST $> 3 \times$ ULN with the appearance of fatigue, nausea, vomiting, right upper quadrant pain or tenderness, fever, rash, and/or eosinophilia ($> 5\%$)

Because transient fluctuations of ALT or AST are common, and progression to severe drug induced- liver injury or acute liver failure is uncommon, automatic discontinuation of study treatment upon finding a greater than $3 \times$ ULN elevation of ALT or AST may be unnecessary. If a drug induced-liver injury is identified, refer to Section [16.6](#) for guidance.

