9. STUDY ASSESSMENTS AND PROCEDURES

9.1. General Instructions

- Study procedures and their timing are summarized in the Schedule of Assessments ([Table 6](#)). Protocol waivers or exemptions are not allowed.
- Results of all protocol-required procedures will be recorded in the eCRF whenever applicable.
- Immediate safety concerns should be discussed with the Medical Monitor immediately upon occurrence or awareness to determine if the participant should continue or discontinue study treatment.
- Adherence to the study design requirements, including those specified in the Schedule of Assessments ([Table 6](#)), is essential and required for study conduct.
- Study visits should be scheduled in the morning, whenever possible.

- All laboratory assessments required by the protocol will be performed by a central laboratory unless otherwise stated.
- For onsite and offsite study visits (refer to Section 9.6 and [Table 6](#)), participants should take their study treatment after blood draws for PK and after all pre-dose assessments and procedures have been completed.

The Investigator will maintain a screening log and enrollment log to record details of all participants screened and to confirm eligibility or record reasons for screening failure, as applicable.

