9.8.4. Efficacy-Related Biomarkers

Samples for biomarker assessments will be collected according to the Schedule of Assessments ([Table 6](#)). Blood, tissue, and stool samples will be analyzed by the central or specialty laboratory. Details for collection, processing, and storage will be provided in the Laboratory Manual. Residual samples will be stored and may be used for additional analyses if the participant has granted consent where allowed by the regulatory authorities and local ethics committees.

C-reactive protein (CRP): CRP is an acute phase protein expressed by hepatocytes in response to inflammatory cytokines and will be assessed using a hs-CRP assay. Investigators will be blinded to the hs-CRP results during the treatment and follow-up periods.

Fecal calprotectin: Fecal calprotectin is a complex consisting of calcium-binding proteins. It is expressed by activated neutrophils (and to a lesser extent by macrophages and monocytes) and fecal levels correlate with the number of neutrophils in the gut. It is used as a biomarker of intestinal inflammation. Investigators will be blinded to the fecal calprotectin results during the treatment and follow-up periods.

Lymphocyte counts: Etrasimod is believed to modulate lymphocyte trafficking resulting in a reduction in peripheral lymphocyte count and lymphocyte availability for recruitment to sites of inflammation. During the treatment period, the Investigator will be blinded to the white blood cell (WBC) and differential counts. During the treatment period, WBC differential results will be assessed by an unblinded Medical Monitor (not providing direct medical oversight of study conduct). If either of the following occur, the unblinded Medical Monitor will notify the Investigator with additional instructions.

- ANC < 1000 cells/ μ L
- ALC < 200 cells/ μ L

If the ANC is confirmed below the 1000 cells/ μ L limit, the Investigator will be requested to closely monitor for serious infection and institute appropriate follow-up at his or her discretion.

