If the ALC is confirmed below the 200 cells/ μ L limit, study treatment should be interrupted and should not be reinitiated if the ALC remains below this threshold. In this situation, the unblinded Medical Monitor will notify the Investigator and provide instructions on additional actions that the Investigator may need to take. When there is at least one measurement of ALC < 200 cells/ μ L, blinded values may be released to treating physicians and Investigators as deemed medically

necessary to monitor infection and/or aid in diagnostic work-up as clinically indicated, and/or as a tool to assess the effectiveness of therapeutic interventions for an infection. Investigators will repeat CBC with differentials weekly until ALC > 500 cells/ μ L.

Re-initiation of the study treatment can only be considered when ALC > 500 cells/ μ L.

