9.9.7. Clinical Laboratory Tests

Refer to [Table 5](#) for the list of clinical laboratory tests to be performed and the Schedule of Assessments ([Table 6](#)) for timing and frequency for each test. All scheduled clinical laboratory tests will be completed by a central lab or a sponsor approved regional lab for analysis unless extenuating

circumstances prevent shipments to a central lab (eg, natural disasters, war, etc.) in which case a qualified local laboratory can perform tests only once permission is granted by the Sponsor (or delegate). If a local laboratory is used for protocol-specified tests (even in parallel), this will be captured as a PD. Laboratory tests for a documented new or ongoing AE are not a PD. Details regarding clinical laboratory sample collection, preparation, and shipment are provided in the Laboratory Manual by the central laboratory.

Clinical safety laboratory tests should be completed predose. The Investigator must review the laboratory report, document this review, and record any clinically relevant changes occurring during the study in the adverse event section of the eCRF (results of the total WBC and ALC will be reviewed and monitored as described in Section 9.8.4). The laboratory reports must be filed with the source documents. Clinically significant abnormal laboratory findings are those that are not associated with the underlying disease, unless judged by the Investigator to be more severe than expected for the participant's condition.

All laboratory tests with values considered clinically significantly abnormal during participation in the study or within 30 days after the last dose of study treatment should be repeated until the values return to normal or baseline or are no longer considered clinically significant by the Investigator or Medical Monitor.

- If such values do not return to normal/baseline within a period of time judged reasonable by the Investigator, the etiology should be identified, and the Sponsor should be notified.
- All protocol-required laboratory assessments, as defined in the Schedules of Assessments (Table 6), must be conducted in accordance with the Laboratory Manual.
- If laboratory values from non-protocol -specified laboratory assessments performed at the institution's local laboratory require a change in participant management or are considered clinically significant by the Investigator (eg, adverse event, SAE, or dose modification), then the results must be recorded in the eCRF.

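### Protocol 5.1 makes eosinophilia with ALT or AST above 3 × ULN a mandatory stop, but 9.8.4 masks the differential from the Investigator and sets no route for reporting eosinophils

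*Protocol*

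**What the plan says.** **The stopping rule.** Protocol 5.1 has a list of reasons for which double-blind treatment must be discontinued. Under suspected drug-induced liver injury it gives four criteria. The fourth is ALT or AST > 3 × ULN with the appearance of fatigue, nausea, vomiting, "right upper quadrant pain or tenderness, fever, rash, and/or eosinophilia" (> 5%). The and/or makes eosinophilia sufficient alone. The text that follows says automatic discontinuation on a rise above 3 × ULN may be unnecessary.

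**The masking.** Protocol 9.8.4, under lymphocyte counts, says: "During the treatment period, the Investigator will be blinded to the white blood cell (WBC) and differential counts". It adds that "WBC differential results will be assessed by an unblinded Medical Monitor (not providing direct medical oversight of study conduct"). It then says "If either of the following occur, the unblinded Medical Monitor will notify the Investigator with additional instructions", and lists ANC < 1000 and ALC < 200 cells/µL. After at least one ALC < 200, "blinded values may be released to treating physicians and Investigators as deemed medically" necessary.

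**Related text.** Protocol 9.9.7 says "The Investigator must review the laboratory report, document this review, and record any clinically relevant changes occurring during the study", with the parenthesis that "results of the total WBC and ALC will be reviewed and monitored as described in Section 9.8.4". Table 5 footnote a is attached to the row for the white cell count with differential. It has the unblinded Medical Monitor review total white cells, neutrophils, lymphocytes and CD4 T cells, with instructions to the site when lymphopenia is significant. It keeps Investigators blinded to the results and refers to 9.8.4 for detail.

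**The concern.** A mandatory stop needs someone who holds every value in the rule, or a stated way of bringing the values together. Here the Investigator, who acts on 5.1, sees ALT and AST but, on the plain wording of 9.8.4, not the eosinophil percentage. The unblinded Medical Monitor sees the differential but is told to notify the site for neutrophils and lymphocytes only. No section assigns anyone to compare eosinophils with 5% when a transaminase passes 3 × ULN, or to report the answer.

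The text after the rule makes the accompanying sign decisive. An Investigator who sees a rise above 3 × ULN and no sign is told that automatic stopping may be unnecessary. A participant whose only sign is eosinophilia could then continue dosing when 5.1 says treatment must end.

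**Working it through.** The plan states no figure on this point, so the check is to set the sections side by side. A short calculation follows for the blinding cost of the fix.

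**1. How much of the rule is affected.** The liver criteria in 5.1 are:
- ALT or AST > 8 × ULN;
- ALT or AST > 5 × ULN for > 2 weeks;
- ALT or AST > 3 × ULN with bilirubin > 2 × ULN or INR > 1.5;
- ALT or AST > 3 × ULN with one of seven signs (fatigue, nausea, vomiting, right upper quadrant pain or tenderness, fever, rash, eosinophilia).

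Only the seventh sign of the fourth criterion uses the differential. The exposed case is therefore ALT or AST > 3 × ULN, not > 8 × ULN, not > 5 × ULN for > 2 weeks, bilirubin ≤ 2 × ULN, INR ≤ 1.5, none of the other six signs, and eosinophils > 5%.

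**2. Who sees what during treatment.**
- ALT and AST: the Investigator. No section masks them, and 9.9.7 requires review of the laboratory report.
- Eosinophils: within the differential that 9.8.4 masks. The placement of footnote a on the differential row fits that reading, although its reference to the results could mean only the four counts it names.
- Unblinded Medical Monitor: assesses the differential, which read literally includes eosinophils. No section says this role receives ALT or AST.

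**3. What triggers a message to the site.** Section 9.8.4 has two triggers, neither on eosinophils. Footnote a has one, on lymphopenia. The stated release of blinded values follows an ALC < 200. None forbids another message; none asks for one on eosinophils.

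**4. Other routes.**
- Section 9.1: "Immediate safety concerns should be discussed with the Medical Monitor immediately upon occurrence or awareness".
- Section 9.9.7: laboratory tests for a documented adverse event are not a deviation, so a local differential is allowed. It is not directed, and it would also show the lymphocytes that the masking protects.
- Section 5.1: stopping by Investigator decision is allowed.
- Appendix 6: closer monitoring above 3 × ULN. Its work-up list for suspected Hy's law cases has no differential.
- Section 3.4: there is no external monitoring committee as a second check.

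Each route is discretionary or does not name eosinophils.

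**5. Blinding cost of reporting the criterion.** Let e be the eosinophil share before dosing, L the lymphocyte share of white cells, and f the fractional fall in lymphocytes, with other counts unchanged. The new share is e / (1 − L × f), which exceeds 5% when e > 5% × (1 − L × f). The documents give no values for L or f, so these are assumptions:
- L = 0.20, f = 0.40: 5 × 0.92 = 4.6%
- L = 0.30, f = 0.50: 5 × 0.85 = 4.25%
- L = 0.40, f = 0.60: 5 × 0.76 = 3.8%

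On these assumptions, a pre-dose share above 3.8% to 4.6% would read as > 5% with no change in eosinophils.

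**The case against.** The strongest case on the other side is that the plan already covers this. Section 9.8.4 sends the differential to an unblinded physician, and nothing bars that person from calling the site. The rule cannot be met without a visible ALT or AST above 3 × ULN, so the Investigator knows there is a liver concern, can read in 5.1 that eosinophils count, and is told in 9.1 to raise safety concerns with the Medical Monitor.

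Much of this stands, and it rules out three stronger readings that a reader might infer:
- *Nobody looks at eosinophils.* Not supported: 9.8.4 has the unblinded Medical Monitor assess the differential. What is missing is an eosinophil limit and an instruction to report.
- *The Investigator has no reason to ask.* Not supported: the transaminase rise is visible and is reason enough.
- *Three sections set three conflicting masking lists.* Not clearly so: 9.9.7 and footnote a both refer to 9.8.4. They leave the extent of masking less plain than it should be.

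What the objection does not supply is a directed step. The Investigator must think to ask for a masked value. Section 9.8.4 describes the unblinded role as outside direct medical oversight of the study, and no section says how such a request reaches it.

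**Conclusion.** The point holds as a narrow gap in a reporting route. If the protocol is followed as written, one of seven signs in one of four liver criteria can be met without the Investigator being told. The stop then rests on an unprompted question, an undirected local test or discretionary stopping. All other liver stopping criteria work as written, so nothing here supports the inference that liver safety monitoring fails in general.

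The conclusion assumes that the differential in 9.8.4 includes eosinophils. If the sponsor meant to mask only the counts named in footnote a or 9.9.7, the Investigator sees eosinophils and 5.1 works; 9.8.4 is then worded too broadly. Either way an edit is due.

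Severity is minor. The documents give no event rate for the exposed case and none is claimed. Efficacy estimates and estimands are not affected.

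**What to change.** Add one sentence to Protocol 9.8.4 and to Table 5 footnote a: *When ALT or AST is > 3 × ULN, the Investigator (or a central laboratory alert) informs the unblinded Medical Monitor, who checks the eosinophil percentage in the same sample and reports only whether the Section 5.1 eosinophilia criterion is met or not met.* The first clause is needed because that role is given no transaminase results. The same sample matters because scheduled visits are 4 weeks apart from Week 4 to Week 12, so waiting for the next one could delay a mandatory stop by that long.

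Also state in 9.8.4 whether eosinophils are masked, and use the same wording in 9.9.7 and footnote a.

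The cost is a brief extra review. The schedule of assessments already has the blood count with differential and the laboratory tests at the same treatment visits, so no new samples are needed there. Lymphocyte values stay blinded. There is a small blinding cost: a drug-related fall in lymphocytes raises the eosinophil percentage, so a report that the criterion is met carries some information on treatment, and some such reports, and the stops that follow, may reflect that fall. The message goes out only for a participant whom 5.1 already requires to stop. SAP 3.1 says the study will be discontinued early, so the change helps only participants still dosing.

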Treatment-emergent adverse events (TEAEs) in the 1 mg, 2 mg, and placebo groups were reported for 59.6%, 56.0%, and 50.0% of participants, respectively; treatment-related TEAEs were reported for 7.7%, 10.0%, and 5.6% of participants, respectively; serious adverse events (SAEs) were reported for 5.8%, 0%, and 11.1% of participants, respectively; and TEAEs leading to discontinuation of study

treatment were reported for 5.8%, 8.0%, and 0% of participants, respectively. No participants died during the study. Overall, the 2 mg dose demonstrated a favorable safety profile and was chosen as the dose for the current Phase 3 program.

Participants may continue existing nonbiologic therapy for UC (eg, 5-ASA, corticosteroids) per the concomitant medication and stable dose criteria. As preexisting background therapy is allowed, a placebo comparator is justified. The 12-Week Induction Treatment Period in the current study is based on the safety and efficacy findings of the Phase 2 APD334-003 placebo-controlled study. The 2-Week and 4-Week Follow-Up visits will provide off-treatment safety information.

The primary endpoint of clinical remission at Week 12 as assessed using the MMS is standard, widely used, and in accordance with the nonbinding US FDA Guidance for Industry, *Ulcerative Colitis: Clinical Trials Endpoints* (FDA 2016). Other endpoints for the study are widely used and considered reliable measures of efficacy and safety. The assessment of exposure in this study will provide further insight to the PK and PD of etrasimod in Japanese UC participants and facilitate bridging analyses efficacy and safety with the global data.

As detailed in Section 10.2, the study is powered to the primary endpoint for demonstrating a statistically significant difference in achieving clinical remission between etrasimod therapy and placebo at Week 12. The 1:1:1 randomization scheme will maximize the number of participants receiving a potentially beneficial therapy.

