Participants who discontinue treatment prematurely, regardless of the reason, should be instructed to return for an ET visit within 7 days of the last administration of study treatment ([Table 6](#)) and complete all of the ET assessments. If a participant discontinues due to pregnancy, they are not required to complete the endoscopy. If the ET visit is within 4 weeks of the last sigmoidoscopy and biopsy, these procedures do not need to be repeated.

If the ET visit is ≥ 2 weeks after the last administration of study treatment, the 2-Week Follow-Up visit is not required; however, the 4-Week Follow-Up visit should be scheduled and completed. If the ET visit is ≥ 4 weeks of the last dose of study treatment, the 4-Week Follow-Up visit is not required unless the ALC is not within normal limits.

If treatment discontinuation is considered an adverse event, refer to Section [9.9.8.3.](#) for AE/SAE reporting guidance.

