9.5. Follow-Up Period

For participants not participating in the OLE study, follow-up visits will be performed at 2 and 4 weeks after the last administration of study treatment as indicated in the Schedule of Assessments ([Table 6](#)).

If the ET or Study Completion visit is ≥ 2 weeks after the last administration of study treatment, the 2-Week Follow-Up visit is not required; however, the 4-Week Follow-Up visit should be scheduled and completed. If the ET or Study Completion visit is ≥ 4 weeks after the last administration of study treatment, the 4-Week Follow-Up visit is not required.

If the absolute peripheral lymphocyte count is not within normal limits at the 4-Week Follow-Up visit, participants should return for CBC with differential according to local standard of care (captured as subsequent Follow-Up visit or unscheduled visit).

All adverse events should be recorded for 30 days after last administration of study treatment (Section [9.9.8.2.2](#)).

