For guidance on monitoring participants with notable lymphopenia, please refer to Section 9.8.4.

See Section 16.6 for suggested actions and Follow-up assessments in the event of potential DILI.

Table 5: Clinical Laboratory Tests

SCREENING Only
Virology HIV, HBsAg, HBcAb , HBsAb, HBV DNA, HCV (RIBA)
Stool Sample Bacterial culture, ova and parasites, C. difficile
Drugs of Abuse Amphetamine, barbiturates, benzodiazepines, cocaine, methadone, methamphetamine, methylenedioxymethamphetamine, opiate, oxycodone, phencyclidine
Others Hemoglobin A1c, Interferon gamma releasing assay (IGRA) (eg, QuantiFERON or T-SPOT-TB)
PREGNANCY TESTING
Serum pregnancy test beta-human chorionic gonadotropin (β -hCG) - Screening Urine β -hCG (only for women of childbearing potential)

Table 5: Clinical Laboratory Tests (Continued)

CLINICAL CHEMISTRY, HEMATOLOGY, AND COAGULATION		
Hematology		Serum Chemistry
Hematocrit	Albumin	Potassium
Hemoglobin	Alkaline phosphatase	Sodium
Mean corpuscular hemoglobin	Alanine aminotransferase	Thyroid-stimulating hormone
Mean corpuscular hemoglobin concentration	Aspartate aminotransferase	Thyroxine free
Mean corpuscular volume	Bicarbonate	Total bilirubin
Platelet count	Blood urea nitrogen	Triiodothyronine free
Red blood cell count	C-reactive protein	Total cholesterol
White blood cell count with differential ^a	Calcium	Total protein
TBNK ^a	Chloride	Triglycerides
Coagulation		Creatinine
Prothrombin time	Creatine kinase	Uric acid
Activated partial thromboplastin time	Direct bilirubin	
International normalized ratio	Glucose	
URINALYSIS		
Appearance	Nitrite	
Bilirubin	Occult blood	
Color	pH	
Glucose	Protein	
Ketones	Specific gravity	
Microscopic examination of sediment	Urobilinogen	
BIOMARKERS		
Lymphocytes ^{a,b}		
hs-CRP ^b		
Fecal calprotectin ^b		
Immunophenotyping		
Proteomics		
STOOL SAMPLE^c		
Ova and parasites, C. difficile		

^a Total WBC, neutrophil, lymphocyte, and TBNK will be available for review prior to randomization. After randomization, the total WBC, neutrophil, lymphocyte, and CD4 T cell counts will be reviewed by an unblinded Medical Monitor who will provide instructions to the site Investigator in the event of significant lymphopenia. Investigators will remain blinded to the results after randomization. Refer to Section 9.8.4 for additional details.

^b Investigators will remain blinded to the results after randomization.

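### For a late early-termination visit, the protocol gives conflicting rules on whether a low lymphocyte count keeps the 4-Week Follow-Up visit and on whether the site may see that count

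*Protocol*

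**What the plan says.** **Waiver of the 4-Week Follow-Up visit**

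- Section 5.1, for an ET visit 4 or more weeks after the last dose: "the 4-Week Follow-Up visit is not required unless the ALC is not within normal limits".
- Section 9.5, for an ET or Study Completion visit at the same distance: "weeks after the last administration of study treatment, the 4-Week Follow-Up visit is not required". No lymphocyte condition is attached. Table 6 footnote b repeats this rule.
- Section 9.5 and footnote b then add a lymphocyte rule of their own: "If the absolute peripheral lymphocyte count is not within normal limits at the 4-Week Follow-Up visit, participants should return for CBC with differential".

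**Who sees the count**

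- Table 5, footnotes a and b (Section 9.9.7): "Investigators will remain blinded to the results after randomization". No end is given. Footnote a has an unblinded Medical Monitor instruct the site if lymphopenia is significant, and refers to Section 9.8.4.
- Section 9.8.4: "During the treatment period, the Investigator will be blinded to the white blood cell (WBC) and differential counts". The same section treats C-reactive protein differently: "Investigators will be blinded to the hs-CRP results during the treatment and follow-up periods".
- Section 9.8.4 sets the lymphocyte level at which the unblinded Medical Monitor notifies the site at below 200 cells/µL.
- Table 6 lists ET together with Week 12, under the 12-week treatment period.

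**The concern.** Two sites could handle identical participants differently and both comply: one brings back a participant with a low count, the other closes follow-up. The rule in Section 9.5 that would bring the participant back is tied to a visit that the same section has just waived, so it gives no protection there.

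The exception in Section 5.1 also works only if someone at the site knows the absolute lymphocyte count (ALC). The protocol does not settle whether the site may see it, and no passage names who relays a count that is below normal but not below 200 cells/µL.

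The protocol gives the purpose of these visits in Section 3.2: "The 2-Week and 4-Week Follow-Up visits will provide off-treatment safety information". A fall in lymphocytes is the expected effect of the drug, and Section 1.3 reports that counts in earlier studies were back to normal within 7 days of the last dose. A count still low at 4 weeks would depart from that experience, and is the kind of finding that should be followed in one agreed way.

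**Working it through.** No power, rate or alpha is involved, so there is no figure in the plan to reproduce. The check is a day count and a comparison of passages.

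**1. Who meets the waiver conflict.** Inputs: ET is due within 7 days of the last dose (Section 5.1); the waiver starts at 4 weeks (Sections 5.1 and 9.5, Table 6 footnote b); the 4-Week visit has a window of ±3 days (Table 6).

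- Waiver start: 4 × 7 = day 28 after the last dose.
- Lateness needed: 28 − 7 = 21 days beyond the limit for ET.
- 4-Week window: 28 − 3 = day 25 to 28 + 3 = day 31.

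| ET visit, days after last dose | 4-Week visit under 5.1 | 4-Week visit under 9.5 and footnote b |
|---|---|---|
| 0 to 7 (on schedule) | required | required |
| 8 to 27 (late) | required | required |
| 28 to 31, ALC normal | waived | waived |
| 28 to 31, ALC low | kept; coincides with the ET visit | waived |
| 32 or later, ALC low | kept; window already closed, so no date is defined | waived |

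The rules differ only in the last two rows. Section 5.1 does not mention the Study Completion visit, which Section 9.5 also covers.

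**2. Whether another rule catches the participant.** Take an ET visit on day 28 or later, with an ALC below normal but not below 200 cells/µL.

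- The return-for-CBC rule in Section 9.5 and footnote b cannot apply, because its trigger visit has been waived.
- Section 9.9.7 asks for laboratory values judged clinically significant to be repeated until they resolve. This is a real second route, but it depends on someone having seen the value and judged it.
- Section 9.8.4 requires weekly CBCs until the ALC exceeds 500 cells/µL, but only once it has been below 200.

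**3. Whether the site can see the count.**

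| Count | Under Table 5 | Under Section 9.8.4 |
|---|---|---|
| At a late ET visit | blinded | unclear: the drug has stopped, but Table 6 files ET under the treatment period |
| At the 4-Week visit | blinded | visible |

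The ET count can therefore be read as blinded under either passage. The 4-Week count is blinded only if Table 5 overrides Section 9.8.4.

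**4. The gap in notification.** The site is alerted below 200 cells/µL, while the follow-up rules turn on the normal range, whose lower limit the documents do not give. SAP Section 18.3.1 tabulates lymphocytes below 0.5 × 10⁹/L, which is 500 cells/µL. Counts from 200 up to 500 are thus of declared safety interest, yet have no stated route to the site while blinding lasts.

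**5. What is still measured.** Table 6 schedules a CBC with differential at Week 12/ET and at both follow-up visits. Blinding changes who sees the result, not whether blood is drawn. At a late ET visit, the ALC at 28 or more days off drug is recorded.

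**The case against.** The strongest reply is that Table 5 is shorthand. Footnote a sends the reader to Section 9.8.4, and so does the text of Section 9.9.7. Section 9.8.4 blinds the differential in the treatment period only, but blinds C-reactive protein and fecal calprotectin in follow-up as well. That contrast looks deliberate. On this reading the site sees the 4-Week count and the Section 9.5 trigger works. This largely answers the concern for the 4-Week count. It does not answer it for the ET count, which Table 6 files under the treatment period, and it leaves the waiver conflict untouched.

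The second reply is rarity: ET must be at least 21 days overdue and the count must still be low, although earlier studies saw recovery within a week. That stands, and it limits the size.

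A reader might go further in three ways that the documents do not support.

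- *Recovery goes unmeasured.* It does not. CBCs are drawn at ET and at any follow-up visit held, and Sections 9.9.7 and 9.8.4 contain other triggers for repeat tests.
- *The recovery table in SAP 18.3.1 is biased towards recovery.* The waiver in Section 9.5 does not depend on the ALC, so it does not select slow recoverers, and the Section 5.1 rule retains them. If blinding cost a repeat CBC after an abnormal 4-Week result, the abnormal value would remain the last one and recovery would look less complete. No direction can be claimed.
- *Everyone outside the open-label extension with a low count is affected.* With ET on schedule, both follow-up visits are required whatever the ET count, and the 2-Week count triggers neither rule.

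**Conclusion.** The protocol contradicts itself on an operational safety rule, and it is wrong as written. Section 5.1 cannot be reconciled with Section 9.5 and Table 6 footnote b for an ET visit at day 28 or later with a low ALC. Table 5 and Section 9.8.4 give different ends to the blinding on which that rule depends.

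The effect is small. It reaches the few participants whose ET visit is at least 21 days overdue and, if Table 5 is taken to override Section 9.8.4, those whose 4-Week count is low. The documents give no numbers for either group. The risk is that a persistently low ALC is followed inconsistently, or that the rule is never applied. Measurement is not lost, and no bias of known direction is shown. The only output touched is a descriptive safety table; no efficacy conclusion depends on it.

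This rests on reading ET as part of the treatment period, as Table 6 lays it out, and on the 200 cells/µL level being the only stated lymphocyte threshold for notifying the site.

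**What to change.** 1. Reconcile Section 5.1, Section 9.5 and Table 6 footnote b to one waiver rule, covering both ET and Study Completion visits. If the rule keeps the visit for a low ALC, say when it is to be held once the day 25 to 31 window has passed.
2. Reconcile Table 5 footnotes a and b with Section 9.8.4 on when blinding to the white cell count and differential ends, and say on which side of that line an ET visit falls.
3. Name who tells the site of an ALC outside the normal range when the site is still blinded, so that whichever trigger is kept can be applied.

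Which clinical rule stands is for the sponsor to decide.

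The cost is a clarification of a few sentences and the table footnotes, with no visit beyond those that one of the passages already requires. SAP Section 3.1 says the study will be discontinued early, so the change may reach few participants. If it comes too late, the study report can state which rule the sites followed.
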